20.7 Safety Analysis

All subjects who receive at least 1 dose of study drug will be included in the safety analyses. Safety data will be summarized descriptively or graphically, as appropriate.

20.7.1 Adverse Events

Adverse events will be coded using the appropriate version of MedDRA. All AEs will be presented in a data listing. Only TEAEs (events that are new in onset or aggravated in severity following treatment) will be included in all summaries. TEAEs will be summarized for each treatment group, by system organ class and preferred term. Serious adverse events (including death) will be summarized. In addition, AEs will be summarized by severity and relation to study drug.

20.7.2 Clinical Laboratory Tests

[figure not shown]
Hematology, blood chemistry, lipid panel, urinalysis and HbA1c results will be summarized at baseline and at each visit by treatment group. Change from baseline to each visit will also be summarized. Abnormal laboratory values will be identified and analyzed.

20.7.3 Vital Signs

Vital sign results (heart rate, diastolic/systolic blood pressures, respiratory rate, and body temperature) and corresponding changes from baseline values will be summarized at each visit with descriptive statistics by treatment group.

20.7.4 Other Safety Analysis

Other safety assessments including physical examinations, weight, and pregnancy testing, will be analyzed with appropriate summary statistics.

20.9 Interim Analysis

An interim analysis will be done when 40% of subjects have completed the Week 24 visit. Details of the interim analysis will be provided in the statistical analysis plan.

20.10 Statistical Power and Sample Size Considerations

The primary efficacy analysis will compare the mean telephone administered ALSFRS-R total score change from baseline at Week 36 in the group treated with Acthar to that in the placebo group using mITT analysis population. With 140 mITT subjects in the group treated with Acthar and 70 mITT subjects in the placebo group (210 subjects total), assuming the expected ALSFRS-R total score change from baseline of 6.3 and 9 in Acthar and placebo groups, respectively, the common SD of the ALSFRS-R total score change from baseline at Week 36 of 5.83 (estimated from PRO-ACT database), and dropout rate of 20% prior to Week 36, the study will have at least 80% power to detect the treatment difference at the 0.05 level of significance. Assuming a few subjects might not qualify for the mITT analysis population after randomization, approximately 213 subjects will be enrolled and randomized into Acthar treated group and placebo group in a 2:1 ratio.

20.11 Missing Data

20.11.1 Imputation for Missing Data

Imputation procedures and key sensitivity analyses will be outlined in the statistical analysis plan.

20.11.2 Sensitivity Analysis

Sensitivity analyses of the primary endpoint will be performed by using different missing data imputation methodologies.

20.12 Deviations From the Statistical Analysis Plan

Any deviations from the planned statistical analysis will be described and justified in the final clinical study report as appropriate.

21 ADVERSE EVENTS AND SERIOUS ADVERSE EVENTS

21.1 Safety

For safety information about Acthar, refer to the most recent version of the Prescribing Information ([Mallinckrodt, 2015](#)) and the Investigator's Brochure ([Mallinckrodt, 2016b](#)).

21.2 Definitions

Adverse Event

An AE is any untoward or undesirable medical occurrence in a subject who is administered an IMP, which does not necessarily have to have a causal relationship with this treatment.

Examples of AEs include but are not limited to:

- Clinically significant laboratory findings.
- Clinically significant changes in physical examination findings.
- An AE occurring due to IMP overdose whether accidental or intentional.
- An AE occurring from IMP abuse.
- An AE associated with IMP withdrawal.
- Unexpected Adverse Event.

An unexpected AE is defined as an AE, the nature and severity of which is not consistent with the applicable product information in the most recent version of the Investigator's Brochure.

Adverse experiences (serious or non-serious) that commonly occur in the study population or background regimen will be considered anticipated events. Such events include known consequences of the underlying disease (disease-related) or condition under investigation (eg,

symptoms, disease progression) and events unlikely to be related to the underlying disease or condition under investigation but common in the study population independent of drug therapy. Anticipated events, when reported, to be associated with the use of the investigational product, are a subset of unexpected adverse events (events not listed in the Investigator's brochure). However, these events do not warrant expedited reporting as individual cases when serious criteria have been met because it is not possible to determine that there is a reasonable possibility that the drug caused the event. As a result, they do not meet the definition of a suspected adverse reaction.

Serious Adverse Event

An SAE is defined as any untoward medical occurrence that results in any of the following outcomes:

- Death.
- A life-threatening AE.
- Inpatient hospitalization or prolongation of existing hospitalization.
- A persistent or significant incapacity or substantial disruption of the ability to conduct normal life functions.
- Results in a congenital anomaly/birth defect.

Important medical events that may not result in death, be life-threatening, or require hospitalization may be considered serious when, based upon appropriate medical judgment, may jeopardize the subject or subject and may require medical or surgical intervention to prevent one of the outcomes listed above. Examples of such medical events include allergic bronchospasm requiring intensive treatment in an emergency department or at home, blood dyscrasias or convulsions that do not result in inpatient hospitalization, or the development of drug dependency or drug abuse.

Death

Death is an outcome of an event. The event that resulted in death should be recorded and reported on the SAE Form. All causes of death must be reported as SAEs. The investigator should make every effort to obtain and send death certificates and autopsy reports to Mallinckrodt.

Life-Threatening Event

A life-threatening event refers to immediate risk of death as the event occurred per the reporter. A life-threatening event does not include an event that, had it occurred in a more severe form, might have caused death but, as it actually occurred, did not create an immediate risk of death. For example, hepatitis that resolved without evidence of hepatic failure would not be considered life-threatening, even though hepatitis of a more severe nature can be fatal. Similarly, an allergic reaction resulting in angioedema of the face would not be life-threatening, even though angioedema of the larynx, allergic bronchospasm, or anaphylaxis can be fatal.

Hospitalization

Hospitalization is defined as an official admission to a hospital. Hospitalization or prolongation of a hospitalization constitutes a criterion for an AE to be serious; however, it is not in itself considered an SAE. In absence of an AE, a hospitalization or prolongation of a hospitalization should not be reported by the investigator as an SAE. Such situations include, but are not limited to, the following:

A hospitalization or prolongation of hospitalization is needed for a procedure required by the protocol.

A hospitalization or prolongation of hospitalization is part of a routine procedure followed by the center (eg, stent removal after surgery). This should be recorded in the study file.

A hospitalization for a preexisting condition that has not worsened.

Note that the following hospitalizations are not considered SAEs in Mallinckrodt clinical studies:

A visit to the emergency department or other hospital department of less than 24 hours that does not result in admission (unless considered "important medical event" or life-threatening event).

Hospitalization for procedures that are electively performed for the management of ALS, such as percutaneous endoscopic gastrostomy tube placement or tracheostomy, in the absence of a true life-threatening situation will not be considered SAEs.

21.3 Adverse Event and Serious Adverse Event Classifications

Study Drug Relatedness

The following classifications should be used when evaluating the relationship of AEs or SAEs to study treatment (Table 21-1).

Table 21–1: Adverse Event Relationships

Relationship	Definition
Related to ALS Disease Progression	A known consequence of the underlying disease related to disease progression with no plausible relationship to the administration of study treatments.
Not Related	No relationship between the experience and the administration of study treatment; related to other etiologies such as concomitant medications or subject's clinical state.
Unlikely Related	The current state of knowledge indicates that a relationship is unlikely.
Possibly Related	A reaction that follows a plausible temporal sequence from administration of the study treatment and follows a known response pattern to the suspected study treatment. The reaction might have been produced by the subject's clinical state or other modes of therapy administered to the subject.
Related	A reaction that follows a plausible temporal sequence from administration of the study treatment and follows a known response pattern to the suspected study treatment and can be confirmed with a positive re-challenge test or supporting laboratory data.

Severity Assessment

For purposes of consistency, if required the investigator may use the intensity grades presented in Table 21-2.

Table 21–2: Adverse Event Severity Grades

Grade	Definition
Mild	Does not interfere with subject's usual function and activities
Moderate	Interferes to some extent with subject's usual function and activities
Severe	Interferes significantly with subject's usual function and activities

If an AE increases in severity (eg, from moderate to severe); decreases in severity (eg, changes from moderate to mild); or there is a change in seriousness, a new AE will be opened and the original AE will be closed. If an AE is still ongoing at the time of a subject's completion of the follow-up visit, the resolution/stop date and time is left blank.

To ensure there is no confusion or misunderstanding of the difference between the terms "serious" and "severe," which are not synonymous, the following note of clarification is provided:

The term “severe” is used to describe the intensity (severity) of a specific event (as in mild, moderate, or severe myocardial infarction); the event itself, however, may be of relatively minor medical importance (such as a severe headache). This is not the same as “serious,” which is based on the subject/event outcome or action criteria usually associated with events that pose a threat to a subject's life or functioning. Seriousness (not severity) serves as a guide for defining regulatory reporting obligations.

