All fields on the AE CRF page should be completed for each event with a full description of the event and date of onset/start and resolution/stop. A medical diagnosis if known, should be recorded in lieu of each individual sign and symptom associated with the diagnosis and experienced by the subject. If no medical diagnosis is known, the term used by the subject to describe the event or signs noted by the site personnel should be recorded.

Serious Adverse Events

Initial Reporting

Serious adverse events (based on FDA/ICH definition of an SAE) require immediate reporting to Global Pharmacovigilance.

- For all SAEs, the investigator, or designee, must complete the SAE Report Form with the minimum information required by FDA and ICH and submit it to Mallinckrodt Global Pharmacovigilance or designee within 24 hours of first knowledge of the event even if the experience does not appear to be related to the IMP.
- The investigator, or designee, will receive acknowledgement of receipt of the SAE Report Form from Mallinckrodt Global Pharmacovigilance or designee.

- Should the investigator or designee have any difficulty in sending the SAE Report, they may contact Mallinckrodt Global Pharmacovigilance or designee based on the information in the Study Operations Manual.
- If there is any doubt about whether the information constitutes an SAE, the information is to be treated as an SAE.

The investigator(s) or designee is required to submit the any Expedited Safety Report or Suspected Unexpected Serious Adverse Reaction to the responsible IRB/IEC.

The sponsor will ensure that any Expedited Safety Report or Suspected Unexpected Serious Adverse Reaction is submitted to the FDA and other regulatory agencies as appropriate.

Follow Up Reporting

The investigator or designee must complete an SAE Report Form for all follow-up information received and submit it to Mallinckrodt Global Pharmacovigilance or designee within 24 hours of receipt. The investigator(s) or designee will receive acknowledgement of receipt for each SAE Report Form from Mallinckrodt Global Pharmacovigilance or designee.

- The investigator or designee is required to provide all related information/supporting documentation of an SAE until the SAE is resolved or stabilized or the subject has been referred to a nonstudy physician for follow-up treatment.
- The investigator(s) or designee is required to submit the Safety Alert to the responsible IRB/IEC.

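### Both positive causality classes in Table 21-1 require a known response pattern, so a well-timed reaction of a new kind has no positive rating, in conflict with Section 21.2

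*Combined protocol and SAP*

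**What the plan says.** Section 21.3 introduces Table 21-1 with the instruction "The following classifications should be used when evaluating the relationship of AEs or SAEs to study treatment". The table has five classes, and no other causality scale appears in the protocol. Both positive classes describe a reaction that "follows a plausible temporal sequence from administration of the study treatment and follows a known response pattern to the suspected study treatment".

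- **Possibly Related** needs plausible timing and also an event that "follows a known response pattern to the suspected study treatment. The reaction might have been produced" by the subject's clinical state or other therapy.
- **Related** needs plausible timing and an event that "follows a known response pattern to the suspected study treatment and can be confirmed with a positive re-challenge test or supporting laboratory data".
- **Unlikely Related** is defined by one sentence: "The current state of knowledge indicates that a relationship is unlikely".
- **Not Related** needs the absence of any relationship and attribution to another cause.
- **Related to ALS Disease Progression** needs a known consequence of the disease with no plausible link to treatment.

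Section 21.2 gives the expectedness rule: "An unexpected AE is defined as an AE, the nature and severity of which is not consistent with the applicable product information", with the Investigator's Brochure as the reference. In its text on anticipated events, the same section refers to events that are reported as associated with the product and are not listed in the Brochure. It decides whether an event is a suspected adverse reaction by whether there is a reasonable possibility that the drug caused it.

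Section 21.4 has the sponsor ensure that "any Expedited Safety Report or Suspected Unexpected Serious Adverse Reaction is submitted to the FDA" and to other agencies. Section 20.7.1 states that "AEs will be summarized by severity and relation to study drug".

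**The concern.** A causality scale in a trial of a drug in a new indication has to be able to register a reaction nobody has seen before. This one makes prior recognition of the pattern a necessary condition for any positive rating, so it handles familiar reactions and leaves new ones without a class.

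The setting makes this more than a drafting quibble. Acthar is not approved in ALS. Section 9.4 says that many approved indications involve short-term use while use in ALS is expected to be chronic. A subject randomised to Acthar who completes the extension receives daily dosing for 36 + 48 = 84 weeks. The earlier ALS experience that Section 9.1 describes is one open-label pilot in 43 subjects, so the stock of known patterns in this population is small. In the 48-week extension every subject receives Acthar, so there is no concurrent placebo comparison and attribution leans more on the individual rating.

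Two things are at stake: whether the investigator's rating marks a new serious reaction as suspected, and where such an event is placed in the summaries by relation to study drug.

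**Working it through.** No arithmetic applies, since the point depends on no sample size, error rate or event count. The check takes one hypothetical event through the definitions: plausible timing, a kind of reaction not previously recognised with Acthar, and no evidence for another cause.

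**Step 1. The two positive classes.**

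| Class | Plausible timing | Known response pattern | Re-challenge or laboratory support | Does the event qualify? |
|---|---|---|---|---|
| Possibly Related | required | required | not required | No: pattern fails |
| Related | required | required | required | No: pattern fails |

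The conditions are joined by *and* in both rows, so strong timing cannot make up for the missing pattern.

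**Step 2. The three remaining classes.**

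| Class | Condition | Does the event qualify? |
|---|---|---|
| Unlikely Related | existing knowledge points against a relationship | No: absence of knowledge is not knowledge against |
| Not Related | no relationship, another cause | No: no other cause identified |
| Related to ALS Disease Progression | known disease consequence, no plausible link to treatment | No: not a known disease consequence |

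Read strictly, the event fits none of the five classes. An investigator who has to choose one would probably take a negative class, most likely Unlikely Related. That last step is an inference about rater behaviour; the text does not compel it.

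**Step 3. Comparison with Section 21.2.** That section contemplates an event that is both absent from the Brochure and reported as associated with the product. The test it implies for a suspected reaction is a reasonable possibility of causation, with no mention of a known pattern. Table 21-1 is therefore stricter than the test in the section before it, and stricter for the type of event that expectedness rules exist to catch.

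**Step 4. Where the rating is used.**

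- *Section 20.7.1:* the summaries by relation to study drug take the rating as input, so the event would probably appear in a negative row.
- *Section 21.4:* recording does not depend on the rating. Every SAE goes to sponsor pharmacovigilance within 24 hours, even if it does not appear related. The sponsor issues and submits SUSARs. No sentence ties that decision to Table 21-1, and none provides a separate sponsor assessment of causality.

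**The case against.** The strongest case on the other side is that little depends on this rating. All adverse events are recorded whatever their relationship to treatment. Every SAE reaches the sponsor within 24 hours. Section 20.7.1 summarises all treatment-emergent events by treatment group, system organ class and preferred term, and summarises serious events as well. The DSMB in Section 11.5 reviews unblinded datasets, and 36 weeks of placebo control can show an imbalance without any causality judgement. All of this stands, and it limits the consequence.

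Three stronger readings are tempting, and the documents support none of them.

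- *The SUSAR pathway cannot operate for a new reaction.* That would require the sponsor's decision to be bound to the Table 21-1 rating, and nothing says so. The sponsor receives the event in any case and could apply the Section 21.2 test.
- *No event can be both unexpected and rated at least possibly related.* Expectedness is judged against the Brochure, but Table 21-1 ties known pattern to no document. An unlisted event in line with the corticosteroid-like effects in Section 9.5 could follow a known pattern and still be unexpected. So could an event of a known kind at unexpected severity, if severity alone is enough under Section 21.2.
- *Such an event must be recorded as unrelated and drops out of the tables.* The negative classes have conditions of their own that the event does not meet. Section 20.7.1 plans a breakdown by relation, so the rating moves an event between rows and does not remove it.

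These points leave the table itself unanswered: as written, it offers no positive class for a reaction of a new kind.

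**Conclusion.** The point holds in a limited form. On a literal reading, Table 21-1 gives a well-timed reaction of a new kind no positive class, and this conflicts with Section 21.2. A rating made on the table would not flag such a reaction as suspected, and the event would probably count on the negative side of the summaries by relation to drug. The SUSAR route loses one signal, the investigator's rating, while SAE reporting and sponsor review remain.

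The size cannot be put as a number. About 213 × 2/3 = 142 subjects are to be randomised to Acthar, but that counts people exposed, not events misrated, and the documents give no rate of new reactions.

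The conclusion rests on two assumptions: that investigators apply the table as worded, and that one without a fitting class chooses a negative one. The effect on SUSARs also depends on whether the sponsor assesses causality separately, which the protocol does not say.

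**What to change.** Edit Table 21-1 and add two sentences to Section 21.4.

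1. **Possibly Related:** plausible timing, with a reasonable possibility that the study treatment caused the event, whether or not the event follows a known response pattern.
2. **Related:** treat known pattern, positive re-challenge and laboratory data as evidence that supports the rating, not as conditions that must all be met.
3. **Section 21.4:** state that both positive classes count as suspected, and that the sponsor applies the same Section 21.2 test when it decides on SUSARs.

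The reasonable-possibility wording is preferable to a looser rule that a causal role cannot be excluded. With daily dosing for 36 to 84 weeks, most events have plausible timing, and the looser rule would take in many events that Section 21.2 would not call suspected.

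The cost is a protocol amendment with IRB/IEC approval under Section 24, a change to the eCRF wording, and somewhat more events rated possibly related. No visit, assessment or sample size changes.

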21.4 Adverse Event and Serious Adverse Event Recording and Reporting

AEs and SAEs will be recorded from signing of the ICF through completion of the follow-up visit. The investigator is required to record the AE or SAE regardless of the severity of the event or its relationship to study treatment. Prior to the Baseline Visit/Visit 2, only AEs and SAEs related to study procedures will be recorded. The investigator must follow up on all AEs and SAEs reported to have occurred 28 days after the last dose of study drug until the event has resolved or stabilized or at such time the investigator refers the subject to a nonstudy physician. The investigator will document the further follow-up information in the subject's source document.

During the period specified above, the investigator will:

- Record all AEs and SAEs from the signing of the ICF through the completion of the End of Study/Early Termination visit.
- Report all SAEs on an SAE Report Form to Mallinckrodt Global Pharmacovigilance or designee.
- Report all pregnancies to Mallinckrodt Global Pharmacovigilance or designee on the Pregnancy Surveillance Form.
- Submit any Expedited Safety Report or Suspected Unexpected Serious Adverse Reaction from Mallinckrodt Global Pharmacovigilance or designee to the IRB/IEC.

The reporting requirements for AEs are summarized in [Table 21-3](#).

Table 21–3: Reporting Requirements for Adverse Events

Seriousness	Reporting Time	Type of Report
All Serious	Within 24 hours of first knowledge of event	Initial report on the SAE Form, appropriate eCRF, and source document
	Within 24 hours of receipt of follow-up information	Follow up report on the SAE Form, appropriate eCRF, and source document
Nonserious	Per case report form submission procedure	Appropriate eCRF and source document

Adverse Events

Adverse events can be reported spontaneously or elicited during open-ended questioning (ie, "How have you been feeling since your last visit?"), examination, or evaluation of a subject. Signs and symptoms must be recorded using standard medical terminology. For subjects incapable of giving consent, the legally acceptable representative may provide information regarding the subject's status.

All fields on the AE CRF page should be completed for each event with a full description of the event and date of onset/start and resolution/stop. A medical diagnosis if known, should be recorded in lieu of each individual sign and symptom associated with the diagnosis and experienced by the subject. If no medical diagnosis is known, the term used by the subject to describe the event or signs noted by the site personnel should be recorded.

Serious Adverse Events

Initial Reporting

Serious adverse events (based on FDA/ICH definition of an SAE) require immediate reporting to Global Pharmacovigilance.

- For all SAEs, the investigator, or designee, must complete the SAE Report Form with the minimum information required by FDA and ICH and submit it to Mallinckrodt Global Pharmacovigilance or designee within 24 hours of first knowledge of the event even if the experience does not appear to be related to the IMP.
- The investigator, or designee, will receive acknowledgement of receipt of the SAE Report Form from Mallinckrodt Global Pharmacovigilance or designee.

- Should the investigator or designee have any difficulty in sending the SAE Report, they may contact Mallinckrodt Global Pharmacovigilance or designee based on the information in the Study Operations Manual.
- If there is any doubt about whether the information constitutes an SAE, the information is to be treated as an SAE.

The investigator(s) or designee is required to submit the any Expedited Safety Report or Suspected Unexpected Serious Adverse Reaction to the responsible IRB/IEC.

The sponsor will ensure that any Expedited Safety Report or Suspected Unexpected Serious Adverse Reaction is submitted to the FDA and other regulatory agencies as appropriate.

Follow Up Reporting

The investigator or designee must complete an SAE Report Form for all follow-up information received and submit it to Mallinckrodt Global Pharmacovigilance or designee within 24 hours of receipt. The investigator(s) or designee will receive acknowledgement of receipt for each SAE Report Form from Mallinckrodt Global Pharmacovigilance or designee.

- The investigator or designee is required to provide all related information/supporting documentation of an SAE until the SAE is resolved or stabilized or the subject has been referred to a nonstudy physician for follow-up treatment.
- The investigator(s) or designee is required to submit the Safety Alert to the responsible IRB/IEC.
- The sponsor will ensure that any Expedited Safety Report or Suspected Unexpected Serious Adverse Reaction is submitted to the FDA and other regulatory agencies as appropriate.

